**STUDY TITLE**

**Reducing time to spaced-out appointments for newly-diagnosed people living with HIV: a pilot study**

**A. OVERVIEW OF THE STUDY**

**Reducing time to spaced-out appointments for newly-diagnosed people living with HIV: a pilot study** is the third part of a three-part research grant entitled, **Minimizing losses from HIV care under Treat All in Rwanda**. This research grant is funded by the US National Institute of Health's (NIH) National Institute of Mental Health (NIMH) and was awarded to the Albert Einstein College of Medicine, NY, US, working in close partnership with Rwanda Military Hospital (RMH). This grant is nested within the **Central Africa International Epidemiology Databases to Evaluate AIDS (CA-1eDEA)**, a research consortium led by Albert Einstein College of Medicine and RMH. The research proposed in this protocol will leverage the existing data and resources of CA-1eDEA, the strong and successful partnership between Albert Einstein College of Medicine and RMH, and ongoing support from an advisory committee that includes senior members of the Rwanda Biomedical Center (RBC). The protocol for CA-1eDEA has previously been approved by the Rwanda National Ethics Committee (RNEC) and the IRB of the Albert Einstein College of Medicine.

Most countries in sub-Saharan Africa have adopted differentiated care models for people living with HIV (PLWH), including Rwanda. Current Rwandan HIV guidelines classify newly-diagnosed PLWH as “unstable”, requiring frequent visits to the health facility. Before they can advance to being “stable” patients, with spaced-out appointments that allow them to visit the health facility less often, they must be on antiretroviral therapy (ART) for 18 months and virally suppressed on two consecutive measurements. Patients face multiple barriers to attending frequent appointments including structural issues (such as distance to the health facility, transportation cost, long waiting times) and facing stigma while traveling to and while at the health facility. Reducing the time newly-diagnosed PLWH spend in the “unstable” category could potentially decrease the burden on patients and the health facility and potentially decrease the costs of frequent appointments. We therefore propose a pilot study to examine the effect of reducing the time from diagnosis to advancement to the “stable” category from 18 to 6 months. We will randomize participants to one of three arms: 1) early spaced-out appointments after 2 suppressed viral loads (advancement to the “stable” category at 6 months if 2 consecutive viral loads are suppressed); 2) early spaced-out appointments after 1 suppressed viral load (advancement to the “stable” category at 6 months if a single viral load is suppressed) or usual care (advancement to the “stable” category at 18 months). We will compare study arms with respect to viral suppression at 12 months (primary outcome) and appointment/pharmacy adherence (secondary outcome). We hypothesize that reducing the time to the “stable” category with spaced out appointments will be feasible, acceptable, not inferior to 18 months with respect to viral suppression or adherence, and will be cost-effective.

**B. OVERVIEW AND SPECIFIC AIMS**

The overarching goal of this research is to increase retention on antiretroviral therapy (ART) among people living with HIV (PLWH) in sub-Saharan Africa, the region most affected by the global HIV pandemic. With the goal of ending the pandemic, the UNAIDS “90-90-90” targets for 2020 are that 90% of all PLWH know their HIV status, 90% of people with diagnosed HIV infection receive sustained ART, and 90% of all people receiving ART achieve viral suppression. While Rwanda is very close to achieving these targets, certain groups such as men and younger PLWH are at higher risk of poorer outcomes. Reducing barriers to initiating and adhering to therapy is thus paramount to ensuring all PLWH in Rwanda succeed in HIV therapy.

In the qualitative work that we have conducted as part of the current research grant, patients reported multiple barriers to attending appointments including structural issues (transportation cost, distance to the health center, long waiting times) and facing stigma while traveling to and while at the

health center. Reducing the frequency of medical appointments for patients who are clinically stable in care could potentially reduce the burden faced by these patients. Indeed, the WHO recommends such an approach to address the specific needs of different groups of PLWH and reduce burden on the health system. While WHO guidelines define “clinically stable” patients as those on ART for 1 year with 2 consecutive viral loads, research studies as well as HIV programs in sub-Saharan Africa have defined “clinically stable” PLWH as those on ART for shorter intervals (i.e. 6 months after diagnosis) and/or with only 1 suppressed viral load. *However, to date, no studies to our knowledge have compared how a shorter time on ART or only 1 viral load measurement compare to the current WHO guidelines.*

The objectives of this study are to thus pilot test the effect of reducing time to spaced-out appointments from 18 to 6 months for newly-diagnosed PLWH in Rwanda. This is a critical time to conduct this work, as most African countries have adopted differentiated care models. Rwanda, where this study is based, was among the first countries to implement Treat All as a national policy and remains a leader in HIV outcomes. To better understand the effects of early spaced-out appointments as well as the degree of viral load monitoring needed to determine stability, we will conduct a 3-arm pilot intervention study. We will enroll 90 patients: 30 will be randomized to 6-month advancement to spaced out appointments after 1 suppressed viral load (at 5 months after enrollment) (“*Early 1*”); 30 will be randomized to 6-month advancement to spaced-out appointments after 2 suppressed viral loads (at 3- and 5-months after enrollment) (“*Early 2*”); and 30 will be randomized to continue in usual care (“*Usual care*”). We will compare the study arms with respect to viral suppression at 12 months after enrollment (primary outcome) and appointment/ pharmacy adherence (secondary outcome). We hypothesize that reducing the time to the “clinically stable” phase to 6 months will be feasible, acceptable, not inferior to usual care with respect to viral suppression or adherence, and will be cost-effective. The specific aims of this study are:

**Aim 1: measure the preliminary efficacy, feasibility and acceptability of early spaced-out appointments.**

- a. Preliminary efficacy: We will compare intervention arms to the usual care arm with respect to 12-month viral suppression (primary outcome) and appointment/pharmacy adherence (secondary outcomes). *Hypothesis: We hypothesize that outcomes will not be inferior in the intervention arms compared to the usual care arm.*
- b. Feasibility. We will examine process measures (patient enrollment, patient waiting time, staff effort) at the end of the trial.
- c. Acceptability. We will assess patient and care provider satisfaction at the end of the trial.

**Aim 2: measure the cost-effectiveness of early spaced-out appointments.** We will collect patient- and health center data on costs, including transportation, specimen testing, and potential cost of downstream outcomes. *Hypothesis: we hypothesize that short-term cost will be higher in the “Early 2” arm compared to “Early 1” and “Usual care,” but that long-term costs will be lower in the “Early 1” and “Early 2” arms compared to the “Usual care” arm.*

## C. RESEARCH DESIGN AND METHODS

### Overview

We will recruit approximately 90 patients and randomize them to one of three arms (early spaced-out appointments after 1 suppressed viral load – *Early 1*; early spaced-out appointments after 2 suppressed viral loads – *Early 2; care as usual*). We will follow patients for 12 months after enrollment. We will compare arms with respect to viral suppression, appointment adherence, and overall cost, as well as collect data on feasibility and acceptability. These findings will inform future Rwandan policy regarding differentiated care for people living with HIV and provide important evidence for global HIV control efforts.

### Central Africa-IEDEA

The NIH-funded Central Africa International Epidemiology Databases to Evaluate AIDS (CA-*le*DEA) consortium is the largest observational HIV research network in Central Africa. In Rwanda, 10 public health centers (HC), one referral hospital and one private HIV clinic collaborate with CA-*le*DEA, under the oversight of Rwanda Military Hospital (RMH), a referral and research hospital in Kigali. Three of these health centers (Gikondo, Kicukiro, Kanombe/RMH) will participate in this pilot study.

### Study setting

The proposed study will be carried out in Gikondo HC, Kicukiro HC, and Kanombe/RMH, as well as Remera HC (a site that does not participate in *le*DEA). These health facilities are located in Rwanda's capital, Kigali, and provide care to approximately 6,000 PLWH. In total, approximately 300 newly-diagnosed patients enroll in these three health facilities each year.

### Study participants, recruitment and enrollment

- **Inclusion/exclusion criteria:** *Inclusion* criteria for the study are: 1)  $\geq 15$  years; 2) newly-diagnosed with HIV; 3) enrolled in care at study health facility; 4) initiated ART. *Exclusion criteria* are: 1) planning on moving away from health center/Kigali in the next 12 months; 2) unable to provide informed consent; 3) enrolled in care while pregnant; 4) co-infected with tuberculosis; 5) concurrent known mental health or substance use disorder.
- **Recruitment:** A study research assistant will work with staff at the health facility to identify persons who are newly-diagnosed with HIV and may be eligible for the study. We will have clinic nurses inform potentially eligible patients about the study during appointments and provide study contact information. We will also put up posters in health facilities with study information.
- **Screening procedures:** The research assistant will meet with interested participants to describe the study and offer enrollment during a follow-up appointment after their enrollment into care. Patients who are interested in participating in the study, who meet criteria and who provide written informed consent will be enrolled in the study and be randomized to either the intervention arms or the standard of care arm.
- **Randomization:** randomization will be stratified by age ( $<24$  vs  $\geq 24$ ) and by clinic and occur in blocks of 4-8, with 1:1:1 allocation of the three study arms.

### Clinical visits: Intervention and usual care arms

- **Early spaced-out appointments after 1 suppressed viral load – Early 1.** Patients enrolled in this arm will pick up medications monthly at the pharmacy and attend clinical appointments every 3 months until 6 months after entering HIV care. They will have a viral load measured at month #5 after entering HIV care. If their viral load is suppressed, they will advance to spaced out appointments at month #6 after entering HIV care, picking up medications every 3 months and attending clinical appointments every 6 months.
- **Early spaced-out appointments after 2 suppressed viral loads – Early 2.** Patients enrolled in this arm will pick up medications monthly at the pharmacy and attend clinical appointments every 3 months until 6 months after entering HIV care. They will have a viral load measured at month #3 and #5 after entering HIV care. If both viral loads are suppressed, they will advance to spaced out appointments at month #6 after entering HIV care, picking up medications every 3 months and attending clinical appointments every 6 months.
- **Standard of care – Usual care.** Patients enrolled in this arm will pick up medications monthly at the pharmacy and attending clinical appointments every 3 months for the duration of the study. They will have a viral load measured at month #5 after entering HIV care.

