**Table 1. Study and research visits**

Study arm	Assessment period (month)											
	0	1	2	3	4	5	6	7	8	9	10	11
Early 1												
Clinic visits	x			x			x					x
Pharmacy pick-up	x	x	x	x	x	x	x		x			x
Viral load						x						x
Early 2												
Clinic visits	x			x			x					x
Pharmacy pick-up	x	x	x	x	x	x	x		x			x
Viral load				x		x						x
Usual care												
Clinic visits	x			x			x		x			x
Pharmacy pick-up	x	x	x	x	x	x	x	x	x	x	x	x
Viral load					x							x
Research visits												
All arms		x				x						x

Data sources and collection:

- **Questionnaires/Surveys:** questionnaires will be administered to participants at each research visit (enrollment, 6 months, 12 months) using RedCap technology. We will collect data on demographics, HIV risk and diagnosis, medication adherence, quality of life, patient satisfaction, and anticipated or experienced HIV-related stigma.
- **Medical records:** we will extract data from participants' medical records, including HIV diagnosis date, ART initiation date, appointment and pharmacy visit dates, and medication regimen.
- **Laboratory/blood testing:** all participants will undergo lab testing including creatinine, CD4 count, liver function testing at study enrollment. Participants will undergo viral load testing at intervals noted above and at the study conclusion at 12 months. Tests will be processed at Rwanda Military Hospital's lab and results will be inputted into study databases and clinical registers.

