### Main outcome variables

- **Preliminary efficacy:** *Primary outcome* is viral suppression (defined as viral load <200) at 12 months (yes/no). *Secondary outcome* is appointment and pharmacy adherence (attended all appointments/missed ≥1 appointment).
- **Feasibility/acceptability:** patient satisfaction with appointment schedule, health worker satisfaction with appointment schedule, patient experiences of stigma
- **Cost:** we will collect data on patient-level costs borne by patient or relatives of the patient towards their care (i.e. transportation to clinic, missed days of work). To ascertain the cost to the health facility, we will estimate fixed (i.e. equipment, human resources) and variable (i.e. type and number of visits, laboratory tests, inpatient care) costs to care.

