### Data analysis

- **Assessment of randomization:** we will compare all covariates between the 3 study arms, using t-tests (or non-parametric tests) for continuous variables and chi-square (or Fisher tests) for categorical variables.
- **Preliminary efficacy:** We hypothesize that viral suppression and appointment/pharmacy adherence will be similar across the 3 study arms. We will first compare proportions of patients achieving viral suppression and attending all appointment/pharmacy visits using chi-square tests. We will use generalized estimating equations to estimate risk differences, risk ratios and associated 95% confidence interval for the effect of each intervention arm compared to the control. The non-inferiority limit will be set at 10%. Because of the small number of participants we will be able to enroll in this pilot study, it may not be sufficiently powered to detect a statistically significant differences in outcomes. However, the findings and the effect size obtained from this study will provide key results on intervention feasibility and guide a future, larger study to test intervention efficacy.
- **Cost analysis:** We hypothesize that the intervention arms will result in reduced patient-level and health-center costs. Outcomes will include: (a) annual cost per patient in each cohort/arm (per patient year cost); and (b) cost-effectiveness of the intervention arms compared with usual care.

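### Does the whole-arm comparison need a companion analysis among participants suppressed at month 5?

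*Combined protocol and SAP*

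**What the plan says.** Under Clinical visits, Early 1 and usual care have the same pick-up and visit frequency until month 6, and the same sentence appears for both arms: "They will have a viral load measured at month #5 after entering HIV care". In Early 1, "If their viral load is suppressed, they will advance to spaced out appointments at month #6 after entering HIV care". Early 2 requires suppression at both month 3 and month 5; usual care has no month-3 load.

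Data analysis estimates risk differences and risk ratios "for the effect of each intervention arm compared to the control", on "viral suppression (defined as viral load <200) at 12 months", with a 10% non-inferiority limit. It warns that the pilot may be underpowered and adds that "the effect size obtained from this study will provide key results on intervention feasibility and guide a future, larger study".

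For feasibility, Aim 1b says: "We will examine process measures (patient enrollment, patient waiting time, staff effort) at the end of the trial". The share advancing is not named there or under Main outcome variables. The laboratory paragraph after Table 1 says that "results will be inputted into study databases and clinical registers", and appointment and pharmacy dates are extracted from medical records.

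**The concern.** Only participants suppressed at month 5 receive the spaced schedule in Early 1. The whole-arm difference is therefore a mixture, and a reader who sees it alone cannot tell a small effect of spacing from a larger effect in an arm where fewer people advanced. That seems to matter because the effect size is meant to inform a larger trial, and because the Specific Aims section introduces the design with the phrase "To better understand the effects of early spaced-out appointments".

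The data for a sharper comparison appear to be at hand. Early 1 and usual care have the same schedule up to month 6 and both have a month-5 load, so one rule could pick out the would-be advancers in both arms before the schedules part. The plan does not use this.

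**Working it through.** **What the planned contrast answers.** The Overview defines Early 1 by the rule itself, advancement at six months given one suppressed load, and Aim 1a compares arms. A comparison of everyone randomized is valid for that question. The Specific Aims phrase leads into the description of the three arms; it does not promise an effect confined to advancers.

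**Inputs.** 30 per arm and the 10-point margin come from the documents (the scale of the margin is not stated; it is taken as a risk difference). The documents give no suppression rates, so these are assumed: share advancing q = 0.70, 0.85 or 0.95; 12-month suppression 95% among those suppressed at month 5, and 55% or 90% among the rest.

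**Dilution.** Whole-arm difference = q·e + (1 − q)·d, where e is the effect among advancers and d is the arm difference among non-advancers. With e = −10:

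| q | d = 0 | d = −5 | d = +5 |
|---|---|---|---|
| 0.70 | −7.0 | −8.5 | −5.5 |
| 0.85 | −8.5 | −9.25 | −7.75 |
| 0.95 | −9.5 | −9.75 | −9.25 |

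Dilution is real in expectation: 3.0, 1.5 or 0.5 points when d = 0.

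**Can one trial of this size show it?** Month-5 suppressed counts were drawn as Bin(30, q) in each arm, with 12-month suppression among them 85% in Early 1 and 95% in usual care, and the rest alike. Over 300,000 or more simulated trials per scenario, the gap between the subset and whole-arm estimates was:

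| q | Expected gap (points) | Chance SD of the gap (points) |
|---|---|---|
| 0.70 | 3.0 | 5.2-8.7 |
| 0.85 | 1.5 | 3.3-6.1 |
| 0.95 | 0.5 | 1.8-3.5 |

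The lower end of each range has the rest at 90%, the upper end at 55%. Noise exceeds signal in every row. Across scenarios, the whole-arm loss was at least as large as the subset loss in 29-45% of trials, so the dilution was hidden or reversed.

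**Precision of the subset.** Its size is 30 × 0.70 = 21 to 30 × 0.95 = 28.5 per arm. Mean Newcombe 95% half-widths with no true effect, in points:

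| q | Whole arm (rest 55% / 90%) | Subset |
|---|---|---|
| 0.70 | 19.1 / 15.1 | 18.4 |
| 0.85 | 17.1 / 14.8 | 16.1 |
| 0.95 | 15.4 / 14.5 | 14.9 |

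The subset is sometimes a little narrower and sometimes wider. Its lower bound lies above −10 in only 13-24% of trials.

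**Added risk of bias.** The subset is defined after randomization and no blinding is described, so knowing the arm could change behaviour before month 5. Tabulating month-5 suppression by arm checks this only weakly: the chance SD of the difference is √(2q(1 − q)/30) = 11.8, 9.2 or 5.6 points. Some month-5 loads may also be missing, since participants may refuse blood tests.

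**The unlisted items.** The share advancing can be read from the visit and pick-up dates and the viral loads already being recorded. The suppression cut-off is stated only for the 12-month outcome, but counting who actually moved to spaced visits does not depend on it. The machine-read Table 1 puts the usual-care load under month 4. It also puts a usual-care clinic visit under month 8 and ends at column 11, which fits a lost or shifted column, so it carries no weight here.

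**The case for a change.** The best case for the addition is that it costs almost nothing and guards against a worse analysis. In a pilot of a conditional intervention, how many people receive it is a basic feasibility result. And if no rule is fixed, someone may later compare Early 1 advancers with all of usual care. With no true effect, that contrast is biased in favour of spacing by (1 − q) × (0.95 − rate in the rest):

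- rest at 55%: 0.30 × 0.40 = 12.0 points, 0.15 × 0.40 = 6.0, 0.05 × 0.40 = 2.0;
- rest at 90%: 0.30 × 0.05 = 1.5 points, 0.15 × 0.05 = 0.75, 0.05 × 0.05 = 0.25.

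Applying the same month-5 rule in both arms removes this bias, and dividing the whole-arm difference by the share advancing is a noisier substitute.

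That warning stands: any comparison among advancers should use one month-5 rule and cut-off in both arms, be limited to Early 1 and usual care, and carry no non-inferiority claim. But the plan proposes no such comparison, so there is nothing to correct. Reporting the share is good practice that a competent analyst would follow without an amendment. Whether to add a small, unblinded, post-randomization subset to a trial that already calls itself possibly underpowered is a matter on which statisticians may reasonably differ.

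**Conclusion.** The concern does not call for a change. The whole-arm contrast is the right primary comparison for a rule of advancing at six months if suppressed. The extra subset would be expected to differ from it by 0.5 to 3.0 points, less than the chance variation of that difference in every scenario examined, so it could not reliably tell a small effect from a diluted larger one. The share advancing is a reporting detail that can be derived from data the study already collects.

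These figures rest on assumed rates (70-95% advancing; 95% against 85% at 12 months among those suppressed at month 5; 55% or 90% in the rest) and on non-advancers faring alike in the two arms. The documents support that last assumption by applying the same adherence intensification to anyone unsuppressed, but they do not state the schedule after month 6 for Early 1 participants who do not advance. If far fewer than 70% advanced, dilution would be larger, but the subset would also be smaller than 21 per arm.

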### Research visits

- All participants will have research visits at baseline (study enrollment, which will occur in the first month after enrollment), month #6 after enrolling in HIV care, and month #12 after enrollment. Participants will undergo interviews at all study visits, and will undergo follow-up viral load testing

at 12 months. Participants will be compensated 8,000 Rwandan francs (RWF), approximately \$8 USD, at each visit.

